3.2 Study Design

This is a randomized, double-blind, placebo controlled phase II trial designed to elicit immune responses to abnormal MUC1. A 1-year booster vaccine will be administered to assess the presence of T cell dependent immune memory. Participants will be randomized on a 1:1 scheme. The protocol will call for injections at week T0, T2, and T10, and a booster injection at week T53. Monitoring of the immune response will be at each time point prior to injection, T0, T2, T10 and at week T12, T52, T55 (post booster), and at the time of the endpoint surveillance colonoscopy up to T156, for a total of 7 measurements of MUC1 immune response. For details regarding study visits and assessments, see Section 7.

Up to 120 participants will be approached for pre-registration, and assuming an 8% ineligibility rate, approximately 110 participants will be randomized to either vaccine or placebo injections and followed up to 3 years for the primary and secondary endpoints. A dropout rate of up to 10% is assumed between baseline and year 1, and an additional 10% drop out rate is assumed between year 1 and year 3 (termination of follow-up).

Eligible participants will have had an advanced adenoma that was completely resected as reported by endoscopic assessment. Advanced adenomas will be defined as: 1) ≥ 1 cm in size; 2) demonstrates villous or tubulovillous histology; or 3) have severe or high grade dysplasia. We anticipate enrolling approximately 4 participants per month across all sites for the first 3-6 months, and then 8 participants per month across all sites until we reach the accrual target. Accrual is expected to be completed in 18 months. Total study duration for Part 1 is expected to be about 22 months, followed by an additional 12 months for Part 2 and 24 months for Part 3.

Intervention Arms: Participants meeting study criteria will be randomly assigned to receive one of two interventions according to the following intervention schedule:

- Muc1/poly ICLC 0.3 mL subcutaneous study vaccine in the upper thigh
- Normal saline injection 0.3 mL subcutaneous in the upper thigh

3.3 Vaccine and Clinical Endpoints

The response to the vaccine will be evaluated by monitoring changes in IgG anti-MUC1 antibody titer ratio; defined as t_{12}/t_0 , where t_0 is the "initial titer" measured prior to vaccination, and t_{12} is the "final titer" drawn at 12 weeks. For the primary endpoint, the titer measured 2 weeks after the 3rd vaccination, at week 12, will be compared to the baseline titer at week 0. Because IgG is more commonly induced and more likely to be detected because of the better quality of reagents, IgG levels will be the indicator of immunogenicity. A titer ratio of ≥ 2 will be considered an immune response. The use of a titer ratio permits a uniform definition for an immunologic response regardless of the baseline level of MUC1 antibody. The titer ratio at week 12 will mark the close of Part 1 of the trial. The assessment of the response to the booster vaccine will be evaluated by examining the week 55 titer to the titer at week 52, prior to receipt of the booster vaccine. Once again, a titer ratio of ≥ 2 for the T55/T52 comparison will be considered a positive immune response.

The titer ratio of 2:1 as a measure of immune response was chosen in part from the infectious disease literature where this ratio is often employed as a marker of immune response. This ratio was commonly attained (44%) in our pilot study in participants with advanced adenoma³⁴. A titer increase of ≤ 2 may also have clinical efficacy. We have no preliminary information to identify what titer ratio may be associated with a clinical endpoint. The measurement of the response to the booster vaccine and communication with the patient regarding response (week 55) will mark the close of Part 2 of the trial.

The week 156 endpoint will be adenoma recurrence. Adenoma prevention trials testing chemoprevention regimens have been performed for a variety of compounds ranging from beta carotene, calcium, folate, aspirin, DFMO, dietary modification, fiber supplementation, etc. Although there have been repeated calls for trials using other intermediate endpoints such as aberrant crypt foci, adenoma recurrence remains the mainstay in examining the efficacy of an agent in relation to colorectal cancer. The adenoma is a reproducible measure, with a reproducible, standardized nomenclature implemented by pathologists.

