2.1 Study Disease: Advanced Adenomas

Advanced adenomas (AAs) are defined as pre-neoplastic adenomatous polyps that are either: 1) ≥ 1 cm in size, 2) demonstrate villous or tubulovillous histology, or 3) have severe or high grade dysplasia. Advanced adenomas occur in about 5-10% of patients undergoing screening colonoscopy. Individuals with AAs are a high risk group. Studies show that individuals having an advanced adenoma have a 2 fold or more risk of having a recurrent AA compared to individuals with non-advanced adenomas^{38,39}, and more importantly, are at higher risk for subsequent colorectal cancer, even years later^{8,40}. Patients with AA are an appropriate group to focus on for prevention. Low levels of anti-MUC1 IgG can be detected in patients with advanced adenomas⁴¹. Most recently, we performed a pilot study of MUC1 vaccine in patients with a prior history of advanced adenoma, though not necessarily recently diagnosed advanced adenomas, and the vaccine was well tolerated with no significant toxicity³⁴.

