2.3 Rationale

Completed Feasibility study of MUC1 Vaccine at U. of Pittsburgh

We enrolled 40 participants who received MUC1/Poly ICLC vaccine at 0, 2, and 10 weeks and antibody titers were evaluated prior to each vaccination and at week 12, 28 and 52³⁴. In the 39 participants that received all three initial doses of vaccine, 17 (44%) had over a two-fold ratio increase at week 12, ten participants had ratios over 4.5 fold, and another 4 participants had a ratio increase from 1.4 – 2.0. The kinetics of the response were similar, with peak antibody levels generally occurring after the third injection. As expected, circulating antibody levels tended to decline over the next year with clearance of the vaccine antigen.

Response to Booster vaccine

To test for the presence of a vaccine-induced T cell memory response, participants received a booster dose of vaccine at 1 year. Of the 16 participants who responded to the initial vaccination and received the booster, 12 (75%) had a two-fold ratio increase when comparing week 54 to week 52. Three of the 4 who didn't have a two-fold elevation at week 54 had maintained high levels of antibody at week 52, hence did not manifest a 2 fold ratio increase at week 54. Overall, the results suggest that responders established a T cell memory response to the MUC1 antigen.

Adverse Events

Over 150 vaccinations were administered in the pilot study. No adverse events above grade 1 were identified, and no unanticipated adverse events were observed. Most participants developed erythema with soreness at the injection site. Some developed short lived fever and muscle aches, which respond well to analgesics such as Tylenol. We had nearly 100% compliance with the study protocol. Participants were monitored with immunofluorescent ANA titers pre vaccination and at 1 year. No participants have developed a change in ANA titer and no new autoimmune diseases were observed.

Figure 2:

[figure not shown]

Figure 2A: Ratio response in MUC1 antibody.
Figure 2B: Kinetics of response to vaccination at 0, 2, and 10 weeks (arrows under x axis) and to booster vaccine at week 52.

Evaluation of Immune Non-Responders

Lack of response to vaccination was correlated with high levels of circulating myeloid-derived suppressor cells but not to circulating T regulatory cells.

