13.4 Primary Objective, Endpoint, Analysis Plan

The primary objective for this study is to compare the ratio of the week 12 to week 0 IgG levels between the MUC1 vaccine and placebo. It is hypothesized that this ratio will be increased in patients treated with the MUC1 vaccine as compared to patients receiving the placebo. Prior data from a pilot study of 39 patients that were treated with the MUC1 vaccine³⁷ showed a mean IgG ratio of 6.46 with a standard deviation of about 10. Assuming equal standard deviations (i.e. 10) across the MUC1 and placebo groups, and assuming up to a 10% drop-out rate by year 1 (presumably less by 12 weeks), retaining at least 50 evaluable participants per arm yields at least 86% power to detect an increase in the mean IgG ratio from 1 to 6.5 for placebo vs. MUC1 (effect size = 0.55), using a 1-sided t-test with a significance level of 0.05. If the data are not normally distributed, we will use the Wilcoxon Rank-Sum test for this primary endpoint analysis. If the vaccine shows a significant increase in the 12-week immune response rate as compared to placebo, we will proceed to Part 2.

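### The primary comparison of T12/T0 uses the baseline titer only as a denominator; adjusting log T12 for log T0 would give a modest, nearly free gain in precision of unknown size

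*Combined protocol and SAP*

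**What the plan says.** The primary objective in Section 13.4 is to "compare the ratio of the week 12 to week 0 IgG levels between the MUC1 vaccine and placebo". The comparison is made "using a 1-sided t-test with a significance level of 0.05", with this fallback: "If the data are not normally distributed, we will use the Wilcoxon Rank-Sum test for this primary endpoint analysis". The sample size statement reads "retaining at least 50 evaluable participants per arm yields at least 86% power", for mean ratios of 1 against 6.5 with a standard deviation of 10 in both arms.

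Section 3.3 sets a ratio of 2 or more as an immune response and adds: "The use of a titer ratio permits a uniform definition for an immunologic response regardless of the baseline level of MUC1 antibody". Section 9.1 describes each patient as his or her own control.

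No section plans a baseline covariate or a log transformation. The week 0 titer is not a stratification factor (Sections 6.8.2.7 and 13.2). Sections 8.1, 13.6 and 13.8 require both titers for a participant to be evaluable, so T0 is known for everyone in the primary analysis. Sections 13.4 and 13.9 make the primary result the decision to enter Part 2. For Part 2, Section 13.5 also plans a comparison of the actual IgG ratio values.

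**The concern.** Dividing by T0 is one way to handle baseline. On the log scale it subtracts log T0 with a coefficient of exactly 1. If the true slope of log T12 on log T0 is below 1, through assay noise, regression to the mean or a ceiling, the ratio over-corrects: low starters tend to show large ratios and high starters small ones. That variation stays in the error term. A chance difference between arms in mean log T0 also passes into the arm contrast, multiplied by (slope − 1). Neither the t-test nor the Wilcoxon test removes it.

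The documents do not establish a slope of 1. Section 2.4 says there are no data on natural fluctuation in antibody level. Section 2.3 gives an example of a ratio limited by its starting value: three of the four pilot responders who did not double after the booster "had maintained high levels of antibody at week 52, hence did not manifest a 2 fold ratio increase at week 54".

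At stake is the precision of the result that decides whether the trial continues, with about 50 evaluable participants per arm.

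**Working it through.** **1. The plan's own figure.** Inputs from Section 13.4: 50 per arm, difference 6.5 − 1 = 5.5, SD 10, one-sided 0.05.

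- Noncentrality: (5.5/10) × √(50/2) = 0.55 × 5 = 2.75, with 98 degrees of freedom.
- Exact one-sided t power: 86.1%. Normal approximation: Φ(2.75 − 1.645) = 86.5%.
- With the unrounded pilot mean (difference 5.46), the exact figure is 85.7%.

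The stated power of at least 86% reproduces.

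**2. Adjusted against ratio analysis on the log scale.** Let ρ be the within-arm correlation of log T0 and log T12, and k = SD(log T12)/SD(log T0). Relative to the log-ratio contrast, the ANCOVA contrast has variance

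k²(1 − ρ²) / (k² + 1 − 2ρk).

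With equal variances (k = 1) this is (1 + ρ)/2. The documents give neither ρ nor k, so the values below are assumptions.

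| ρ (k = 1) | Relative variance | Reduction |
|---|---|---|
| 0.5 | 0.75 | 25% |
| 0.7 | 0.85 | 15% |
| 0.9 | 0.95 | 5% |

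As a guide only: multiplying the planned variance (10²) by these fractions would move the 86.1% to 93.4%, 90.6% and 87.6%. This carries a log-scale fraction over to a raw-scale calculation, so it shows the order of size and is not a forecast.

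**3. When the gain shrinks or vanishes.** Write b = ρk for the slope, set SD(log T0) = 1, and let V be the residual variance of log T12. The relative variance is then V / (V + (1 − b)²).

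- If b = 1 there is no gain, for example with ρ = 0.5 and k = 2.
- If varied vaccine response, unrelated to T0, adds spread to T12, V rises, b is unchanged and the gain falls. With b = 0.5 and k = 1, V = 1 − 0.25 = 0.75 and the relative variance is 0.75/1.00 = 0.75. With b = 0.5 and k = 2, V = 4 − 0.25 = 3.75 and it is 3.75/4.00 = 0.94, a reduction of only about 6%.

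Some spread is likely in the vaccine arm, where Section 13.5 expects about 40% to respond.

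**4. Simulated power.** Settings are assumed: 50 per arm, one-sided 0.05, log SD 0.8, vaccine arm a mixture of responders and non-responders, robust (HC3) standard errors, 2,000 runs each.

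| Vaccine arm | ρ | Log-ratio t-test | ANCOVA |
|---|---|---|---|
| 20% respond | 0.5 | 46% | 50% |
| 20% respond | 0.7 | 57% | 59% |
| 20% respond | 0.9 | 80% | 81% |
| 44% respond, about 3-fold | 0.5 | 83% | 89% |
| 44% respond, about 3-fold | 0.7 | 94% | 95% |

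At 44% and ρ = 0.9 there was no change. With 40% responding and a larger assumed response (mean log-fold 1.8, SD 0.8), both analyses had 98% power or more and differed by at most about 1.5 points. Over the settings tried, the gain ran from 0 to 8 points, with type I error near 5%.

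The log-ratio t-test isolates the effect of adjustment, but it is not a planned test. Against the planned tests:

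- **Wilcoxon.** ANCOVA had higher power in the mixtures above (for example 50% against 36%, and 89% against 78%), though part of that gap comes from the type of test. This fallback is likely to apply: a positive ratio with mean 6.46 and SD about 10 must be strongly skewed.
- **Raw-ratio t-test.** The result was mixed. In responder mixtures that test often had equal or higher power.

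**The case against.** The strongest reply is that nothing here is wrong. Under 1:1 randomization an unadjusted comparison of ratios is valid, the ratio already uses T0, and the stated power is right on its inputs. All of that stands.

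A reader might infer more than the documents support:

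- **That Section 3.3 rests on a false premise of independence from baseline.** The sentence directly follows the cut-off of 2 and says that one definition applies to everyone, which is true. Section 13.4 does not cite it as a reason to omit a covariate.
- **That the pilot shows T12/T0 depends on T0.** The booster observation concerns week 54 over week 52 in three people whose starting level was high after vaccination. For entry levels, Section 2.1 says only: "Low levels of anti-MUC1 IgG can be detected in patients with advanced adenomas". It reports neither their spread nor any relation to the ratio. The booster data show that a ratio can depend on its start; they do not show that this one does.
- **That 5% to 25% of the sample could be saved.** Those figures need equal variances and an assumed correlation. At the response rate the protocol expects, with a large response, the power gain is negligible.
- **That ANCOVA beats the planned t-test.** The simulations do not show this on the raw scale. The claim is limited to precision on the log scale.

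It is also fair that log-scale ANCOVA changes the quantity estimated, and that part of its merit comes from the logarithm and not from the covariate. What survives is that a slope of 1 is assumed without evidence when it could be estimated from data already required.

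**Conclusion.** The point holds as a modest loss of precision. It is not a bias, an error in the power calculation or a fault in the responder definition. The primary analysis treats division by T0 as sufficient handling of baseline and so fixes a slope that the documents leave untested.

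The size is unknown. The 25%, 15% and 5% reductions rest on equal log variances and assumed correlations of 0.5, 0.7 and 0.9. The reduction is smaller where varied response unrelated to T0 spreads T12, and zero at a slope of 1. Simulated power gains over the log-ratio t-test were 0 to 8 points.

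The case for acting is that T0 is available for every evaluable participant, the price at a slope of 1 is about one degree of freedom, and the result decides entry to Part 2.

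**What to change.** **Section 13.4.** Prespecify as the primary analysis an ANCOVA of log T12 on arm with log T0 as covariate and robust standard errors. Keep the one-sided 0.05 level and report the adjusted geometric mean ratio with the 95% confidence interval that Section 13.8 promises. Keep the Wilcoxon comparison of T12/T0 as supportive. Write this in before unblinding, since an adjustment added later would look data-driven.

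**Section 13.5, Part 2.** Use the same form, log T55 adjusted for log T52, for the comparison of actual IgG ratio values. T52 follows three injections, so randomization does not balance it. The adjusted result compares arms at equal pre-booster titer; describe it that way and show it beside the unadjusted T55/T52 comparison.

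**Section 3.3.** No change needed.

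**Cost.** No new samples, visits or participants. The reported effect becomes a geometric mean ratio instead of a difference in mean ratios. The power statement (1 against 6.5, SD 10) then describes only the supportive comparison of raw ratios, and the documents give no log-scale SD or correlation to replace it. The pilot measured both titers (Section 2.3), so its data could supply these for vaccinated participants, though not for placebo. A rule is also needed for values that are zero or negative after the control-well subtraction in Section 10.2.2; the ratio has the same difficulty when T0 is the value affected.

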4. PARTICIPANT SELECTION

4.1 Pre-Registration

4.1.1 Pre-Registration Inclusion Criteria

- 4.1.1.1 History of at least one of the following conditions in the previous 12 months:
 - Colorectal adenoma(s) ≥ 1 cm in maximal diameter
 - Colorectal adenoma(s) with villous or tubulovillous histology
 - Colorectal adenoma(s) with high grade (severe) dysplasia.
- 4.1.1.2 Presumptive evidence that all adenomatous lesions, including qualifying advanced adenoma, have been completely removed.
- 4.1.1.3 Age 40 - 70 years of age at time of registration/randomization. Note: Individuals under the age of 40 with advanced adenomas have a high risk of familial disease. Individuals over the age of 70 begin to show signs of impaired immune function due to age.
- 4.1.1.4 Ability to understand and the willingness to sign a written informed consent document.
- 4.1.1.5 Willingness to undergo screening tests and procedures.
- 4.1.1.6 Willingness to provide blood samples for toxicity monitoring and research purposes.
- 4.1.1.7 Not pregnant or nursing. Note: A negative (serum or urine) pregnancy test must be documented ≤ 7 days prior to registration/randomization for women of childbearing potential.
- 4.1.1.8 Willingness to employ adequate contraception through Week 53 of the study. Note: The effects of the MUC1 vaccine on the developing human fetus at the dose specified in this study are unknown. For this reason, women of childbearing potential and men must agree to use adequate contraception (hormonal, barrier method of birth control, abstinence) prior to study entry and for the period of active vaccination (through Week 53). Should a woman become pregnant or suspect she is pregnant while participating in this study, she should inform her physician immediately.

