4.1.2 Pre-Registration Exclusion Criteria

- 4.1.2.1 History of any colorectal cancer
- 4.1.2.2 History of other malignancy \leq 5 years prior to the Registration/Randomization evaluation, with the exception of basal cell or squamous cell skin cancer.
- 4.1.2.3 Presence of an active acute or chronic infection or uncontrolled illness including, but not limited to unstable congestive heart failure, unstable angina pectoris, cardiac arrhythmia, or psychiatric illness/social situations that would limit compliance with study requirements.
- 4.1.2.4 Acquired immunosuppressive diseases such as active HIV infection or congenital diseases of immunity.
- 4.1.2.5 History of heritable cancer syndrome (FAP, HNPCC).
- 4.1.2.6 History of auto-immune disease such as, but not restricted to, inflammatory bowel disease, systemic lupus erythematosus, rheumatoid arthritis, ankylosing spondylitis, scleroderma, multiple sclerosis, Hashimoto's thyroiditis, or Grave's disease.
- 4.1.2.7 Current or planned use of immunomodulators including: infliximab, 6-MP (mercaptopurine), methotrexate, cyclosporine, or other immunomodulatory drugs.
- 4.1.2.8 History of allergic reactions attributed to compounds of similar chemical or biologic composition to the study agent.
- 4.1.2.9 Pregnant women, because the teratogenic or abortifacient effects of the study agents remain incompletely defined.
- 4.1.2.10 Breastfeeding women, because there is an unknown but potential risk for adverse events in nursing infants secondary to treatment of the mother with the study agents.
- 4.1.2.11. Diagnosis of nonalcoholic steatohepatitis (NASH) and a NAFLD (nonalcoholic fatty liver disease) activity score (NAS) \geq 5. NOTES and EXCEPTIONS: NAS is based on findings from a liver biopsy. Participants with NAS of \leq 2 are eligible for enrollment. Participants with NAS of 3-4 must be discussed with the Principal Investigator and DCP before enrollment to consider other risk factors (i.e., obesity, alcohol intake). Participants with a prior diagnosis of NASH and no available NAS must be discussed with the Principal Investigator and DCP before enrollment to considered risk factors (i.e., obesity, alcohol intake). See Appendix F.

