5.7 Adherence/Compliance

5.7.1 All vaccine/placebo will be administered by appropriately trained study personnel at each site. Vaccine/placebo administration will be documented on the Intervention Administration CRF.

5.7.2 Individuals who receive the Week 0, Week 2, and Week 10 injections will be considered evaluable for the primary endpoint. Individuals who receive the Week 53 injection will be considered evaluable for the Part II key secondary endpoint. Individuals from whom data and specimens are collected for a subsequent clinical colonoscopy occurring at least 1 year (52 weeks) after the Week 0 injection will be considered evaluable for the Part III key secondary endpoint.

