4. Operative notes, endoscopy reports, and/or pathology reports must be reviewed locally to confirm that the candidate meets at least one of the entry criteria specified in inclusion criterion 4.1.1.1. Participants will need to registered/randomized within 1 year from the initial polyp removal, unless evidence of an advanced adenoma is identified at the subsequent colonoscopy, in which case the timing for eligibility will start anew. Note: if

- participants are scheduled for early repeat colonoscopy, such as within 12 months of the colonoscopy that identified the advanced adenoma, to insure complete removal of the qualifying lesion, they should be enrolled after that repeat colonoscopy insures that no residual adenoma is present.
5. Endoscopy report and/or pathology report confirming qualifying advanced adenoma diagnosis as well as the fact that all polyps and adenomas have been removed must be submitted by FAX or email to the CPN Quality Assurance Specialist (QAS) within 30 days after registration/randomization.
 6. Pregnancy test (serum or urine) will be performed for female participants of childbearing potential at baseline/screening and prior to each injection (Week 0, 2, 10, and booster vaccine). Week 0 pregnancy test does not have to be repeated if ≤ 7 days since baseline/screening test. Should a woman become pregnant or suspect she is pregnant while participating in this study, she should inform her study physician immediately.
 7. Week 2 injection may not occur less than 14 days after Week 0 injection. It may occur up to 28 days after the Week 0 injection.
 8. Week 10 injection should occur 7-10 weeks (ideally 8 weeks) after Week 2 injection.
 9. Week 53 booster should ideally occur as soon as possible after the week 52 monitoring test results are available. It may occur up to 4 weeks after the Week 52 visit.
 10. Telephone contact will be made to monitor concomitant medications, possible adenoma recurrence, and the timing of follow up surveillance colonoscopy.
 11. The Risk, Regret, and Symptom Questionnaire (Appendix D) will be administered before the Week 0 injection, after the Week 53 injection, and at the Week 156 visit. The Was It Worth It (WIWI) Questionnaire (Appendix C) will be administered during the Week 55 visit.

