7.4 Evaluation at Completion of Study Intervention

The final blood tests for immune response and toxicity monitoring will take place at Week 55. Those results will be provided, and discussions of adverse events and concomitant medications will take place at Week 57 by telephone,

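### The contraception criterion stops at the Week 53 booster, leaving 0 to 6 days of required cover after an on-time last dose, although its stated reason is unknown fetal effects

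*Combined protocol and SAP*

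**What the plan says.** Criterion 4.1.1.8 opens with "Willingness to employ adequate contraception through Week 53 of the study". Its note gives the reason: "The effects of the MUC1 vaccine on the developing human fetus at the dose specified in this study are unknown". It then says that "women of childbearing potential and men must agree to use adequate contraception" "prior to study entry and for the period of active vaccination (through Week 53"). The exclusion of pregnant women in 4.1.2.9 has a similar basis: "the teratogenic or abortifacient effects of the study agents remain incompletely defined".

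Week 53 is the protocol's name for the booster. Section 7.3 places the four injections at weeks 0, 2, 10 and 53, and 5.7.2 defines the Part II evaluable group as "Individuals who receive the Week 53 injection". The actual date can move. Section 7.1 lets the Week 52 visit fall 51 to 54 weeks after the first injection, and its note 9 lets the booster follow that visit by up to 4 weeks.

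Pregnancy tests for women of childbearing potential are scheduled at screening and "prior to each injection (Week 0, 2, 10, and booster vaccine"), with none later. Criterion 4.1.1.8 and note 6 of 7.1 also ask a woman who becomes pregnant, or suspects it, during the study to tell her physician at once.

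Safety follow-up continues after the booster. Section 7.4 says "The final blood tests for immune response and toxicity monitoring will take place at Week 55" and adds an adverse event telephone call at Week 57. The stopping rule in 13.7.1 covers the first 57 weeks.

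**The concern.** The requirement and the dosing end together. The stated reason, that effects on a fetus are unknown, applies as much to the days after the fourth dose as to the days after the first three, yet the criterion requires almost nothing after the fourth.

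The inclusion of men sharpens this. For a woman, contraception up to the booster helps to avoid dosing someone already pregnant. For a man it has no such role: it can only guard against a partner conceiving after he has been dosed. By binding men, the criterion already treats time after a dose as relevant.

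At stake is participant safety. Someone who follows the criterion exactly could stop contraception at, or within days of, the last dose. No later pregnancy test is scheduled, and none of the follow-up described asks specifically about pregnancy in a participant or a partner.

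**Working it through.** The plan gives an end point (Week 53) but no figure for cover after the last dose, so the check is date arithmetic on the visit schedule, in days from the first injection.

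**Inputs**
- On-time booster: 53 × 7 = day 371 (7.3).
- Booster 4 weeks after an on-time Week 52 visit: (52 + 4) × 7 = day 392 (7.1, note 9).
- Latest permitted booster, after a Week 52 visit at 54 weeks: (54 + 4) × 7 = day 406, or week 58 (7.1, visit timing table and note 9).
- Week 57 call: 57 × 7 = day 399, ± 7 days (7.1).

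**Week 53 read as the booster visit.** The requirement ends with the injection, whenever that is. Cover after an on-time booster is 371 − 371 = 0 days. If the wording is taken to run to the end of that week, it is 377 − 371 = 6 days.

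**Week 53 read as a calendar limit.** Cover = end of requirement − booster day. A negative value means that the requirement ended before the last dose.

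| Booster | Day | Limit at day 371 | Limit at day 377 |
|---|---|---|---|
| On time | 371 | 0 | +6 |
| On-time Week 52 visit, booster 4 weeks later | 392 | −21 | −15 |
| Latest permitted | 406 | −35 | −29 |

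The visit reading is the more natural one, because the criterion equates its end point with the period of active vaccination. It is also the kinder one to the plan. Neither reading gives more than 6 days after the last dose.

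**Comparison with the plan's own follow-up.** For an on-time booster, the Week 55 blood tests fall (55 − 53) × 7 = 14 days later and the Week 57 call 399 − 371 = 28 days later (21 to 35 with its window).

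**The case against.** The best defence is that the rule is coherent as written. It covers every injection, and with a test before each one it serves a clear aim: do not inject a pregnant participant. No section states a washout or a fetal-risk interval, so any period after the last dose is a judgement. That aim does not explain why men are bound, and it is narrower than the reason the criterion gives.

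Several parts of the defence do stand:
- The 28 days come from general follow-up. The Week 55 tests are blood counts and transaminases, and the Week 57 contact is a telephone call; neither measures reproductive risk. The pilot's antibody decline over the following year (2.3) does not supply a fetal-risk interval either.
- The gaps of 14, 56 and 301 days after doses 1 to 3 might be read as a safety margin that was dropped for dose 4. They are only the intervals to the next injection or, after dose 3, to the booster.
- Pregnancy is not wholly unmonitored, since a woman must report it throughout participation. But this acts after conception and does not reach men's partners.
- A reader might infer that participants are told they may stop on booster day. The consent pages were not available, so what participants are told cannot be known. The point concerns the criterion's text alone.

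**Conclusion.** The concern holds as a minor participant-safety point. The criterion gives 0 to 6 days of required contraception after an on-time last dose. On a calendar reading, the requirement could end 29 to 35 days before the latest permitted booster. Both results rest only on the protocol's schedule and windows.

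A reader might infer that a known fetal hazard is being left uncovered, or that many participants are exposed. The documents support neither. They give no fetal-risk data, so the harm cannot be sized. Eligibility is limited to ages 40 to 70, and the sex split, the number of women of childbearing potential and the number of men with such partners are not given, so the number exposed cannot be determined. Nor does the point bear on the results: no endpoint, power calculation or analysis changes.

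**What to change.** In 4.1.1.8, both in the opening sentence and in the note, replace the Week 53 end point with: through at least 28 days after the actual date of the last injection. Counting from the actual date settles the visit-or-calendar question and stays correct when the booster is late.

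At the existing Week 57 call, ask about pregnancy in the participant or a partner. If the booster was late, time the call from the actual injection date as well. Align the consent form if it gives the same end point.

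The 28 days are a practical minimum, matched to the nominal interval from booster to Week 57 call; the sponsor may set a longer period. The cost is a wording change, one added question, and about 4 more weeks of contraception for the participants concerned. No new visit or test is needed.
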